2.3 GOALS AND OBJECTIVES (SCIENTIFIC AIMS)

Neurofibromatosis type 1 (NF1) is a dominantly inherited disorder occurring with a prevalence of 1/3,000 individuals. Patients with NF1 have an increased risk of osseous complications, including tibial dysplasia and tibial pseudarthrosis (TPA) with chronic fracture and non-union. Although occurring in only 2-5% of NF1 patients, management of TPA is fraught with difficulty, with many patients requiring multiple surgeries and up to 33% eventually requiring amputation. Significant evidence from both animal models and human tissue documents a difference in bone biology in NF1, with decreased ability to form new bone as well as increased resorption and remodeling of bone. An international working group of NF specialists and orthopedic surgeons has been formed, and proposes a clinical trial to document efficacy of an osteogenic agent (INFUSE; recombinant human bone morphogenetic protein-2) as a supplement to surgical approaches to TPA in NF1. This international group is committed to successful completion of this trial.

PRIMARY AIMS:

Specific Aim 1: To determine if use of an osteogenic agent (rhBMP-2) at the time of surgical treatment of TPA in NF1 patients will result in improved bone healing when compared to patients treated with the same surgical protocol but without BMP-2.

Specific Aim 2: To document safety of BMP-2 in a pediatric NF1 population

Specific Aim 3: To collect, process, and preserve biologic specimens at the time of surgery for future studies related to NF1.

Primary Objectives:

Objective 1: To perform a phase 2 single-blind, randomized clinical trial to determine if use of INFUSE (rhBMP-2 on a collagen sponge) applied at time of surgical repair of TPA in NF1 patients will result in:

1a. Improved bone healing rates compared to patients treated without INFUSE, based on radiographic evidence of cortical bone union at 12 months after surgery (RUST score; **Primary Outcome Measure at 12 months**)

1b. Shorter time (months) to objective radiographic union than in patients treated without INFUSE.

Objective 2: To evaluate the feasibility and potential toxicities of BMP-2 administration in this population.

Objective 3: To collect, process, and preserve biologic specimens at the time of surgery for future studies.

SECONDARY AIMS/OBJECTIVES:

- To evaluate quality of life at the time of surgery, and at 6 months and 12 months after surgery.

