4.0 METHODOLOGY

4.1 Overview of Proposed Study

This phase II, single-blind, randomized study will evaluate children with neurofibromatosis type 1 (NF1) who undergo surgical management of tibial pseudarthrosis. The rationale is predicated on the observation that union of tibial fracture in patients with NF1 is difficult to achieve without extraordinary measures to optimize bone healing, and that deficits in bone formation as well as excessive bone resorption occur in NF1. The preliminary success in improved rate of tibial fracture healing when rhBMP-2 is locally applied intra-operatively, as outlined by [name] et al. (2010), has influenced the need for a carefully controlled clinical trial to document efficacy and safety of this device. Outcomes of this trial will likely influence surgical decisions in management of patients with NF1 and TPA.

Children with NF1 and TPA whose primary orthopedic surgeon deems surgical intervention is required are eligible for this trial. At time of enrollment, participants will be offered participation in a preference arm or randomized arm, and will be assigned to the BMP-2 or control group based on these choices. Surgery must take place at one of the participating consortium sites, and the standard surgical approach will include: extensive resection of abnormal pseudarthrotic

material, tibial osteotomy, placement of an intramedullary rod, and autogenous bone graft from the iliac crest to the osteotomy tibial gap. Those in the BMP-2 group will in addition have INFUSE in a collagen sponge wrapped around the tibia during the surgical process.

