4.2.3 Enrollment procedures

The NF Clinical Trials Consortium will enroll subjects in this trial. Selected subjects with NF1 and tibial pseudarthrosis will be enrolled at the participating sites where surgery is anticipated. Personnel at the UAB NF Clinical Trials Consortium Operations Center will coordinate enrollment with the participating site, and ensure that eligibility requirements are met, prior to scheduling of surgery and shipment of rhBMP-2. As part of the consent process, patients and families will be provided information about the research aspect of this prospective clinical trial.

Study Modification: Enrollment: Patients may be enrolled on the study once all eligibility requirements for the study have been met. All patients/parents will discuss the study in detail with their surgeon, and will view a Powerpoint presentation about the study with a study coordinator present. **At the time of enrollment, parents/patients will be offered to choose either the Choice Arm or Randomized Arm of the study.** Those selecting the Choice Arm will be assigned to their treatment of choice (either BMP or Control). Those who choose the Randomized arm will be randomly assigned at a 2:3 ratio to BMP or Control group. It is

expected based on prior experience that more patients are likely to prefer the BMP arm. Therefore, the mildly unequal randomization of 2 BMP: 3 Controls is planned to improve the ability to achieve adequate controls for the study. For those in the Randomized arm, assignment will be accomplished by accessing a password controlled website maintained by the DMAC. The website is 21 CFR 11.10(d) compliant for FDA clinical trials.

That website will assign a new subject to a treatment group determined by a randomization list produced by the study statisticians employing a permuted block design. Randomization will be stratified by age (≤ 8 vs > 8 years) and prior surgery (Y/N). Enrollment and randomized treatment assignment must occur before the date of surgery but should be as close to the date of surgery as feasible.

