Blinding: For subjects in the Choice Arm, all subjects, parents, and surgeons will of necessity be **unblinded** to the patient's treatment status of BMP versus no BMP. For those in the Randomized group, all subjects, parents, radiologists, data recorders, and (non-surgeon) site PIs will be **blinded** with respect to the treatment status of each participant. Only the surgeon and one study coordinator or OR tech (designated to deliver the device to the OR) at the site will be aware of the treatment status. If the surgeon is also the site PI, then that site PI will be unblinded. For the measurement of outcome measures, the radiology panel calculating the RUST score and all data recorders will be blinded to the treatment status of all participants. Therefore, **calculation of the primary outcome measure will be blinded for all participants, ensuring a non-biased measure for the primary study outcome.**

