5.4 QUALITY OF LIFE ASSESSMENTS

Pediatric Outcome Data Collection Instrument (PODCI)

An important outcome measure of clinical trials in treatment of tibial pseudarthrosis is quality of life. Many individuals with TPA undergo multiple surgical interventions with long rehabilitation times, precluding their participation in school and recreational activities. In preliminary studies performed by collaborators [name] and [name], an outcomes trial led by [name] (Shriners Research Grant #9165; Multi-Center Study of Outcome of Tibial Dysplasia in NF1 Patients) used the pediatric outcome data collection instrument (PODCI) to evaluate the quality of life of individuals with NF1, with and without tibial dysplasia. The PODCI consists of five domains, with a number of items in each domain [Daltroy et al, 1998; Vitale et al, 2001]. Twenty-three individuals with NF1 with tibial dysplasia were compared to 63 NF1 individuals without tibial dysplasia. Notably, the Basic Mobility normative scores, the Sports and Physical Function scores, and Global Functioning were significantly decreased ($p<0.001$) in NF1 with tibial dysplasia with the mean score for cases about one-third of controls [Stevenson and [name], 2009]. The PODCI has also been reviewed by the REINS committee (Response Evaluation in Neurofibromatosis and Schwannomatosis), and found to be an appropriate outcome measure for this population. **These data demonstrate that the PODCI is an effective QOL measure that can be used to investigate outcome for treatment of TPA in the NF1 population**, and can accompany more traditional clinical measures such as union, range of motion, leg length discrepancy, and limitation of walking distance. Other measures of quality of life have been implemented for the NF1 population [Krab et al., 2009] and the orthopedic community [Vitale et al., 2001; Furlong et al., 2005]; however, these measures have not been applied to the pediatric NF1 population with orthopedic issues.

- Quality of Life will be assessed using the Pediatric Outcome Data Collection Instrument (PODCI) questionnaire. The PODCI is a comprehensive orthopedic-specific instrument (Pencharz et al., 2001) comprised of over 100 questions and takes 15-20 minutes to

complete. Quality of Life Questionnaires are to be completed by patient and parents as follows at baseline, at 6 months, and at 12 months.

- PODCI Pediatrics-parent/child: baseline and follow-up (completed by the parent for all children 2-10 years old).

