As we noted above, we expect that most of the data from this study will be generated by the choice arm and hope to maintain at least 10 randomized controls. We will compare the participant characteristics as well as Rust Scores between any controls identified by choice to those controls by randomization and more importantly RUST scores between the choice and randomized BMP treated arms. We will look at the overlap of the confidence intervals and test the equivalence of the two sets of results using two one sided tests of equivalence at the 5% level with an equivalence margin of 0.513. The margin of equivalence of 0.513 was derived based on the hypothesized difference between treatment and control originally planned and assuming these scores are normal continuous variables. Here we used the midpoint of each Rust Scoring Interval (5.5, 8.5 and 11) and computed the average Rust score for each group based on the hypothesized distribution in each group and ended up with a mean of 9.675 in the BMP group compared to 8.135 in the control group yielding an average difference in Rust Score of 1.54. We took 1/3 of the difference between the treatment average Rust score and the usual care Rust score ending up with an equivalence margin of 0.513. Since these sample sizes are small, we don't expect to reject the null hypothesis of differences as the power is probably low, but if they are different we understand that pooled results will be difficult to interpret. If these

tests of Choice versus Randomized treatment arms are not able to reject nonequivalence, we understand that this is not strong evidence for a lack of poolability between choice and randomization. Nevertheless, it will be sufficient to allow a comparison and calculation of the differences between the treatments and an overall assessment of the benefit of BMP in healing especially if we can demonstrate equivalence. Sensitivity analyses will be conducted using pooled and unpooled results as no statistical evidence of a lack of nonequivalence is not absolute evidence for nonequivalence.

Analyses:

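### The design is still labelled single-blind and randomized although most families are expected to choose and know the treatment; quality of life and pain are not clearly planned to be reported by cohort

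*Combined protocol and SAP*

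**What the plan says.** **Label.** Section 2.3, Objective 1: "To perform a phase 2 single-blind, randomized clinical trial to determine if use of INFUSE". Section 4.1 opens: "This phase II, single-blind, randomized study will evaluate children with neurofibromatosis type 1".

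**Allocation and blinding.** Under section 4.2.3, Choice Arm families receive the treatment they ask for. For the others, "Those who choose the Randomized arm will be randomly assigned at a 2:3 ratio to BMP or Control group". On blinding, the same section says "For subjects in the Choice Arm, all subjects, parents, and surgeons will of necessity be" unblinded, whereas subjects and parents in the Randomized Arm stay blinded. The RUST panel is blinded for all participants. Section 6.2 acknowledges the lost blinding in the Choice Arm and answers it by pointing to that panel.

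**Balance of data.** Section 6.2, Generalizability: "we expect that most of the data from this study will be generated by the choice arm", with the hope of keeping at least 10 randomized controls.

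**Reported outcomes.** Section 5.4: "Quality of Life Questionnaires are to be completed by patient and parents as follows at baseline, at 6 months, and at 12 months". The parent completes PODCI for ages 2 to 10; parent and patient both complete it for ages 11 to 18. The Faces Pain Scale-Revised (FPS-R) is self-reported from age 4. Section 4.2.4 expects most patients to be under 7, so the usual PODCI respondent is a parent.

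**Analysis.** Section 6.2 combines the two cohorts for the primary analysis and promises sensitivity analyses within each. The surrounding detail concerns RUST and participant characteristics. For quality of life and pain, the Analyses paragraph gives summary statistics, paired t-tests of change from before surgery, and mixed models. It names neither a treatment-group comparison nor a split by cohort.

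**The concern.** The label describes the trial as it stood before families could choose. A parent who asked for BMP-2 and knows the child received it may report better function, and the child less pain, without any biological effect. The plan deals with this for the radiographic endpoint and is silent for the outcomes where the respondent's knowledge matters most.

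Section 4.1 says quality of life will be obtained for the two experimental groups, so a reader of the final report will probably look for a BMP-versus-control difference. If that difference pools the cohorts and appears under the current label, it would be read as blinded and randomized evidence when most of it may be neither.

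**Working it through.** The plan gives no figure for reporting bias. Its one related statement, that most data will come from choosers, can be checked.

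**1. Share of choosers**

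Inputs: 10 randomized controls (section 6.2), ratio 3 control to 2 BMP (section 4.2.3), total 36 to 52 (section 6.2).

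- Randomized patients = 10 / 0.6 = 16.7, of whom 10 × 2/3 = 6.7 receive BMP.
- Share of choosers = 1 − 16.7/N.

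| N | Share of choosers |
|---|---|
| 36 | 54% |
| 41 | 59% |
| 46 | 64% |
| 52 | 68% |

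This agrees with the plan's statement. It depends on the number randomized: at N = 52 the share falls below half once 16 controls are randomized (16/0.6 = 26.7 randomized, 49% choosers).

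**2. Which outcomes are exposed**

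| Outcome | Who rates it | Blinded, Randomized Arm | Blinded, Choice Arm |
|---|---|---|---|
| RUST, time to union | Central panel | Yes | Yes |
| PODCI | Parent; also patient from age 11 | Yes | No |
| Pain (FPS-R) | Child from age 4 | Yes | No |

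**3. Illustration of size**

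The shift is an assumption: choosers of BMP report 0.2 to 0.5 SD better, with no true effect. The documents give no value.

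Bias in the pooled difference = shift × (share of choosers in BMP − share of choosers in control), if choosers in both groups shift equally towards a better report.

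- *26 BMP v 10 control, all controls randomized.* BMP choosers = 26 − 6.7 = 19.3, a share of 0.74; the control share is 0. Bias = 0.2 × 0.74 = 0.15 SD to 0.5 × 0.74 = 0.37 SD.
- *26 v 26, 10 controls randomized.* Control choosers = 16, a share of 16/26 = 0.62. Bias = 0.2 × (0.744 − 0.615) = 0.03 SD to 0.5 × (0.744 − 0.615) = 0.06 SD.

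The bias therefore depends on imbalance in choosing between the groups. The plan expects such imbalance, since it anticipates more families preferring BMP.

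**4. Precision of the family-blinded comparison**

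At about 7 BMP v 10 control, SE = √(1/7 + 1/10) = 0.49 SD. The 95% half-width with 15 degrees of freedom is 2.13 × 0.49 = 1.05 SD.

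**The case against.** **Objective 1 is radiographic.** Parts 1a and 1b concern union and time to union, both taken from centrally scored films. This stands. A reader might infer that the stale label means the primary result is open to reporting bias; the documents do not support that, because the panel is blinded for both cohorts.

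**No between-group test is planned for these measures.** This also stands. A reader might turn the illustration into an inflated error rate. At 26 v 10 with no control-choosers, a one-sided 5% test would be positive about 10 to 25% of the time, and a two-sided test about 7 to 17%. Those figures belong to a test that section 6.2 does not specify for quality of life or pain; the one-sided level is given for RUST. They should not be quoted as a property of the plan.

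**A cohort split may already be covered.** The sentence in section 6.2 promising separate analyses within the Choice and Randomized cohorts is not expressly limited to RUST. So the plan cannot be said to rule out a split, and pooling of these outcomes is an inference from silence. What remains is that the split is not clearly stated for PODCI or pain.

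**The data are not wholly open-label.** Correct. In the 26 v 10 case about 17 of 36 families (46%) are randomized and blinded, so partly unblinded is the accurate description.

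**The preference design is disclosed.** Sections 1.0, 4.1, 4.2.3 and 6.2 all describe it, so a careful reader will not be misled for long. That lowers the importance of the point but does not make the label in sections 2.3 and 4.1 correct.

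**Conclusion.** The point holds in a limited form. The label in sections 2.3 and 4.1 contradicts sections 4.2.3 and 6.2: an expected 54 to 68% of patients would be neither randomized nor family-blinded, given 10 randomized controls at 3:2. PODCI and self-reported pain lack the protection that RUST has, and the plan does not clearly commit to showing them by cohort. A pooled treatment comparison of them could favour the chosen treatment.

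The size is unknown. The 0.15 to 0.37 SD figure rests on an assumed 0.2 to 0.5 SD shift and on no family choosing control; with equal shifts and 26 v 26 it drops to 0.03 to 0.06 SD. Severity is minor: secondary outcomes only, and no effect on how RUST is read or on its power.

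**What to change.** 1. In sections 2.3 and 4.1, replace the single-blind, randomized label with: *partially randomized preference trial with blinded radiographic assessment*.
2. In section 6.2, add: *The separate Choice and Randomized analyses also cover PODCI and pain. Any BMP-versus-control difference in these outcomes is reported by cohort with a 95% CI and labelled family-blinded (Randomized) or unblinded (Choice). Pooled results are described as partly unblinded.*
3. In the same edit, reconcile the pain instrument and visit times. The Analyses paragraph of section 6.2 names a PedsQL pain questionnaire and has quality of life and pain measured before surgery and at 3, 6 and 12 months. Sections 5.4 and 5.8 and Appendix I specify the FPS-R at baseline, 6 weeks and 3, 6 and 12 months, and PODCI at baseline, 6 and 12 months.

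I would not make the Randomized estimate the only one interpreted. At about ±1 SD that is a debatable trade for a secondary outcome, and clear labelling is enough.

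Cost: wording and one table split by cohort. No new patients, visits or data. The downside is that the family-blinded estimate will be imprecise, and the report will have to say so.

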3.0 BACKGROUND AND SIGNIFICANCE

Neurofibromatosis Type 1 and Tibial Pseudarthrosis: Neurofibromatosis type 1 (NF1) is an autosomal dominant disorder whose features involve many systems, including skin (cafe-au-lait spots, cutaneous neurofibromas), central nervous system (learning disabilities), musculoskeletal, and tumor predisposition. Up to 38% of patients with NF1 have one or more skeletal abnormality [Crawford and [name], 1999], including long bone dysplasia, scoliosis, sphenoid wing dysplasia, and bone cysts. We have proposed a clinical trial for a rare osseous complication of NF1, tibial pseudarthrosis (TPA), which presents with significant morbidity for patients and extreme difficulty in surgical management.

3.1 Prevalence of the Problem: NF1 occurs with a prevalence of 1/3000 in all populations regardless of ethnicity, race, or gender [Huson et al, 1988; Friedman and Riccardi, 1999]. Tibial pseudarthrosis (TPA) is a relatively rare complication of NF1; data from a large international NF1 database has documented tibial pseudarthrosis to occur in between 2-5% of patients with NF1 [Friedman and Birch, 1997], resulting in a maximum estimated prevalence of 1/60,000 individuals. With a US population of 315 million, there are only estimated to be 5,250 individuals in the US with tibial pseudarthrosis related to NF1, qualifying it as an **orphan disease**.

Tibial pseudarthrosis is defined as a chronic non-union in a bone which has fractured. It can occur in the general population as well as in patients with NF1, although more than half of all individuals with TPA have NF1. In patients with NF1, TPA typically occurs in a bone which is congenitally dysplastic, presenting as an anterior-laterally bowed tibia and/or fibula which has a high risk for fracture. Stevenson et al. [1999] surveyed a multi-center cohort of patients with NF1 and tibial dysplasia and found that tibial dysplasia was 1) most often unilateral, 2) evident in the first year of life, and 3) affected males more often than females by a ~2:1 ratio. Additional findings demonstrated that tibial pseudarthrosis usually results as a progression from tibial anterolateral bowing. This anterolateral bowing is recognized as **tibial dysplasia**, whereas the non-union of bone after fracture is defined as **tibial pseudarthrosis** (Figure 1). Analyses in the report by Stevenson et al. [1999], which reviewed a total of 160 NF1 subjects, showed that 61-66% of individuals with tibial dysplasia progressed to fracture and pseudarthrosis. The average age of fracture was 4.6 years with a range of 0 to 28 years, and the average number of surgeries in cases with pseudarthrosis was 3, with some patients having as many as 10 surgical procedures.

Figure 1 A and B: Radiographs of tibial dysplasia

TPA in NF1 patients leads to major morbidity, including possible lower leg amputation. Presently, best care guidelines for the treatment of TPA in NF1 do not include medical management protocols. We have assembled a multidisciplinary team of clinicians who provide specialized care for patients with NF1. Principal investigators of this clinical trial participated in two clinical trial strategy meetings for treatment of bone abnormalities in NF1 (New York City, 02/2008 and 4/2011) [Elefteriou et al., 2009], which led to a consensus to prioritize the development of a clinical trial for the combined medical/surgical treatment of tibial pseudarthrosis (TPA). Drs. [name], [name], and [name] recruited [name] to jointly work with the NF Clinical Trials Consortium to develop a multi-center clinical trial that implements medical treatment combined with well-established surgical protocols to optimally manage tibial pseudarthrosis in NF1 patients.

3.2 Pathophysiology

The pathophysiology of bone manifestations in NF1 is not yet fully elucidated, although recent research with animal models and human tissues has made great progress in our understanding of this area. The *Nf1* gene is classified as a tumor suppressor gene [reviewed in [name] et al., 1993]. Its encoded product, neurofibromin, is a 240-kDa peptide [reviewed in Sherman et al., 1998] that stimulates the intrinsic hydrolysis of ras-bound guanosine triphosphate (GTP) [Martin et al., 1990]. Ras is a small intracellular protein that must be attached to the inner membrane of the cell to be active in signal transduction. When bound to GTP, the protein transduces growth signals to the cell's nucleus through both mitogen-activated protein kinase (MAPK) and AKT signaling. MAPK signaling cascades are operational in the key cells playing a role in bone homeostasis, remodeling, and fracture healing: osteoclasts and osteoblasts [Chaudhary and Avioli, 1998; Hipskind and Bilbe, 1998]. While *NF1* haploinsufficiency is associated with tumor predisposition, studies support the hypothesis that *NF1* haploinsufficiency also results in a range of non-tumor phenotypes [Wu et al., 2006], including skeletal abnormalities [Alwan et al., 2005]. Osteopenia has been reported in both children and adults with NF1, and is one of the recognized manifestations of this underlying bone disorder [Illes et al. 2001; Kuorilehto et al. 2004; Stevenson et al 2007]. More localized osseous manifestations also occur, including sphenoid wing dysplasia, bone cysts, pectus excavatum, and scoliosis (both idiopathic and dystrophic forms). Bi-allelic inactivation of the *NF1* gene in surgically resected pseudarthrosis tissue has been demonstrated in at least 6 NF1 patients to date [Stevenson et al., 2006; Lee et al., 2012], which suggests that somatic genetic changes contribute to abnormal bone

remodeling and pseudarthrosis in NF1. It is likely that generalized bone changes in NF1 (such as short stature and osteopenia) are related to haploinsufficiency of neurofibromin, whereas focal changes such as tibial dysplasia are related to bi-allelic inactivation of *Nf1*. Bone is regulated by two competing forces: anabolism (new bone formation) and catabolism (bone resorption). The cell types driving these two processes are osteoblasts and osteoclasts, respectively. Osteoblasts, derived from mesenchymal stem cells, are stimulated to produce bone matrix by Bone Morphogenetic Proteins and other growth factors. Osteoclasts are derived from the macrophage/monocyte lineage, and play a major role in bone resorption and remodeling. Neurofibromin is expressed in multiple cell types involved in bone development, including osteoblasts, osteoclasts, chondrocytes, and vascular endothelial cells. Substantial evidence shows a role for dysfunction of both osteoblasts and osteoclasts in NF1-related bone disease [reviewed in Schindeler and [name], 2008]. This cumulating data in both human and animal tissues **documents significant differences in bone biology in NF1, leading to poor bone formation as well as overly active bone resorption, and justifying a therapeutic trial that addresses these issues in NF1 tibial pseudarthrosis.**

